1.0 Introduction

The Optisure™ Lead Post Approval Study (Optisure Lead Study) is a multi-center post-approval study of the Optisure family of high voltage (HV) leads.

The product under study is a St. Jude Medical lead available with a DF1 or DF4 connector, active or passive fixation method and single or dual shocking coils. The goal of this post approval study is to characterize the chronic performance of the St Jude Medical (SJM) Optisure family of right ventricular (RV) HV leads.

2.0 Purpose

The purpose of this post approval study is to characterize the chronic performance of the SJM Optisure family of HV leads in patients that have an approved indication, as per ACC/AHA/HRS/ESC guidelines, for implantation of an ICD or CRT-D system for treatment of heart failure or life-threatening ventricular tachyarrhythmia, and who meet all the inclusion/exclusion criteria. The Optisure lead study will be performed in compliance with the Conditions for Approval as agreed upon with the FDA. If during the course of the study a future generation of the Optisure RV lead is approved, these devices may be included in the study upon agreement with the FDA.

The following objectives will be evaluated in the post approval study:

1. To determine the Optisure lead related complication free rate at 5 years
2. To document all Optisure lead related adverse events

Additionally, the following objectives will be evaluated in a subset of patients in the Optisure lead study who agree to participate in a sub-study:

1. To determine the incidence of externalized conductors after enrollment
2. To determine the incidence of other visual lead anomalies by each subcategory per Appendix A after enrollment
3. To determine the incidence of electrical dysfunction[§] after enrollment
4. To evaluate the 30-day adverse event rate associated with lead revision procedures (include lead extractions or abandonments with or without lead replacement)
5. To determine the prevalence of “other insulation anomalies” in returned Optisure leads:
 - Internal abrasion short under RV shock coil
 - Internal abrasion short under SVC shock coil
 - Exposed conductors defined as a breach of the outer insulation and/or breach of the internal silicone lumen tubing, but the conductor cable is contained within the lead body diameter.

[§]”Electrical dysfunction” is determined to be present after adjudication of the following cases of potential electrical failures that led to the lead being either surgically capped/extracted or electrically abandoned. Potential electrical failures include the following:

- Presence of non-physiologic noise not due to external interference
- Rise in pace/sense (p/s) conductor impedance to $> 2000 \Omega$ or increase of more than 200Ω over previous 6 months or increase of 400Ω over any period of time
- Decrease of more than 200Ω over previous 6 months or to impedance $< 200 \Omega$ from baseline impedance $> 300 \Omega$ or decrease of 400Ω over any period of time
- Change in any high voltage coil impedance of $> 25 \Omega$ or to $> 125 \Omega$ or $< 20 \Omega$
- Capture threshold $> 5 \text{ V}$ or an increase of $> 2 \text{ V}$ from baseline (all measurements) of $< 1 \text{ V}$

NOTE: In all cases, external sources of “noise” and other header-connector causes would be excluded. Functional abnormalities, including exit block and physiologic oversensing in the presence of an electrically intact lead are not electrical failures.

3.0 Description of Device

The Optisure HV lead is an 8 French, transvenous, steroid eluting, bipolar lead intended for the permanent sensing and pacing of the right ventricle, and the delivery of cardioversion/defibrillation therapy when used with a compatible SJM ICD or CRT-D device.

Optisure Model Number	Connector Type	Fixation	Single/Dual Coil
LDA220	DF-1/IS-1		
LDA220Q	DF4	Active	Dual
LDA230	DF-1/IS-1		
LDA230Q	DF4	Active	Dual
LDA210	DF-1/IS-1		
LDA210Q	DF4	Active	Single
LDP220	DF-1/IS-1		
LDP220Q	DF4	Passive	Dual
LDP230	DF-1/IS-1		
LDP230Q	DF4	Passive	Dual

As compared to the Durata leads, the Optisure HV dual coil leads have an increased Optim sheath thickness of $0.0070"$ (from $0.0035"$) between the connector boot and the SVC defibrillation coil. In order to accommodate the increase in the thickness of the Optim sheath, minor modifications have been made to increase the inner dimensions of the suture sleeve. The Optisure HV dual coil leads also have an Optim sheath underneath the SVC defibrillation coil. In order to accommodate the Optim sheath underneath the SVC defibrillation coil, the SVC defibrillation coil has an increased diameter of $0.100"$ (from $0.092"$).

As compared to the Durata leads, the Optim sheath thickness in the Optisure family of HV single coil leads has been increased by 0.0035" between the connector boot and the proximal portion of the lead body, which is 9.85" from the distal tip of the lead.

4.0 Clinical Protocol

4.1 Study Design and Scope

The Optisure lead study is a multi-center, post-approval study that will be performed in compliance with the Conditions for Approval, as agreed upon with the FDA. Patients will be permitted to enroll in the study up to 30 days post-implant of the Optisure lead. Following a successful implant, patients will be followed every 6 months until 60 months (5 years). After patients complete 60 months of follow-up, their participation in the study will end. Patients who are consented prior to implant and for whom an implant is unsuccessful will be followed for 30 days for any adverse events and then withdrawn from the study, or may have an implant reattempted if the physician and patient choose to do so.

Patients who meet inclusion/exclusion criteria, sign an IRB/MEC approved informed consent, and have an implanted Optisure RV lead or attempted implant of the Optisure RV lead will be considered to be enrolled in the study. A total of 1725 patients will be enrolled at a maximum of 60 centers. Enrollment is expected to be completed between 20 and 24 months depending on the rate of enrollment.

Enrollment will be proportional to actual sales, and enrollment duration will not exceed 24 months. If implantation at the study sites is higher than the projected estimates (see section 4.5), then the study enrollment period will be decreased proportionately. Reporting will occur per section 6.0 of the protocol. In order to accomplish this, the study will be conducted at a maximum of 60 study centers.

4.2 Definitions

The following definitions will be used in the Optisure lead study.

- **Abnormal Lead Defibrillation Impedance:** Measured high voltage impedances with values $\leq 20 \Omega$ or $\geq 100 \Omega$
- **Abnormal Lead Pacing Impedance:** Measured pacing impedances with values $\leq 200 \Omega$ or $\geq 2000 \Omega$
- **Adverse Event:** Any unfavorable clinical event which impacts, or has the potential to impact the health or safety of a patient caused by or associated with a study device or intervention. Adverse events are classified as complications or observations.
- **Cardiac Tamponade:** Confirmed or suspected accumulation of fluid in the pericardial space leading to hemodynamic compromise.

- **Cardiac Perforation:** An excursion of the lead through the myocardium. Signs and symptoms of perforation by an intra-cardiac lead may include radiographic evidence of excursion of the lead into the pericardial sac, abnormal echocardiography indicative of a perforation, the accumulation of fluid in the pericardium, cardiac tamponade, or patient symptoms..
- **Complication:** An adverse event that requires invasive intervention to resolve (e.g., lead fracture)
- **Diaphragmatic/Phrenic Nerve Stimulation:** Electrical activation of the diaphragm muscle by the device output pulse. The abrupt diaphragmatic contraction is noted clinically as hiccups associated with each pacing stimulus. The pacing stimulus may stimulate the diaphragm either directly or indirectly via the phrenic nerve.
- **Elevated Pacing Thresholds:** Voltage thresholds $> 3.0V$ at implant or 2-fold increase between visits (after lead maturation) leading to a threshold greater than 3.5V at follow up. This definition is intended to serve as a guideline and it is understood that individual patients may have unique situations.
- **Externalized Conductor:** The appearance on x-ray or fluoroscopy of conductors outside of the lead body due to an abrasion-related breach of the outer insulation.
- **Generator Malfunction:** A confirmed failure of the device to perform as indicated.
- **Lead Dislodgement:** The movement of a pacing lead from its originally implanted position; often associated with changes in pacing and/or sensing thresholds including loss of sensing and/or capture. Dislodgement can often be confirmed by radiographic studies.
- **Lead Fracture:** A break in a conduction cable or coil of a pacing or defibrillation lead typically evidenced by an increase in impedance, intermittent or complete loss of capture, intermittent or complete loss of sensing, noise on the intra-cardiac electrogram and rarely, by visual signs of conductor coil fracture on x-ray.
- **Lead Insulation Damage:** A disruption to the integrity of the lead insulation without disruption of the conductor cable(s) or coil observed visually, electrically, or radiographically. An insulation break may be indicated by a drop in impedance, and can cause loss of capture or high voltage therapy delivery or sensing problems.
- **Loss of Capture:** The inability of the device's output pulse to result in depolarization and contraction of the appropriate cardiac chamber. Causes include insufficient stimulus strength, separation of the electrode from the myocardium, some anti-arrhythmic medications and placement of the stimulating electrode in contact with a non-responsive portion of the myocardium such as scar tissue. Delivery of an output pulse at a time when the myocardium is physiologically refractory is not loss of capture, since capture is not physiologically feasible.
- **Loss of Sensing:** A condition in which the pulse generator is unable to sense intrinsic cardiac signals (applicable to RA and RV leads).

- **Observation:** Adverse events that can be managed without invasive intervention (e.g., oversensing or loss of pacing capture, which is remedied by reprogramming of the pulse generator).
- **Oversensing:** The detection of inappropriate electrical signals by the pulse generator's sense amplifier. These signals, such as myopotentials, electromagnetic interference, T waves or crosstalk between atrial and ventricular channels, must be of sufficient duration to interfere with normal device function (applicable to RA and RV leads).
- **Pneumothorax:** An accumulation of air in the pleural cavity due to a disruption of the pleural lining.
- **Re-Attempted Implant:** Implant is being re-attempted in a new procedure due to previous failed implant of the Optisure lead
- **Re-Implant:** Implant is being attempted in a new procedure because of a previous removal of the Optisure lead implanted at enrollment, e.g. due to infection.
- **Successful implant:** An Optisure lead is implanted.
- **Undersensing:** The failure of the pulse generator to sense P or R waves, causing delivery of inappropriately timed, asynchronous or competitive output pulses. Undersensing can sometimes be corrected by programming the device to a more sensitive setting, i.e., decreasing the millivolt (mV) value. (Applicable to RA and RV leads).
- **Unsuccessful implant:** An attempted implant that does not result in a successful Optisure lead implant.

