5.0 Study Outcome Measures

5.1 Primary Outcome Measure

5.1.1 Freedom from RV Lead Related Complications

The primary outcome measure for the Optisure Lead Post Approval study is the complication free survival rate at 5 years for complications related to the Optisure RV leads.

The hypothesis is as follows:

H0: Complication free survival at 5 years \leq 92.5%

H1: Complication free survival at 5 years $>$ 92.5%

The desired outcome is to reject the null hypothesis. The null hypothesis will be rejected at the 5% significance level if the 95% Lower Confidence Bound (LCB) for the freedom from complications is greater than 92.5%.

Sample Size

Assuming that the time to first complication follows an exponential distribution and the complication-free survival at 5 years is 95%, a sample size of 645 patients provides 80% power to reject the null hypothesis of 92.5% complication-free survival years at the 5% significance level (See Appendix D for detailed sample size calculations).

Patient Group

All patients who had an attempted implant of the Optisure RV lead will be included in the analysis of this endpoint.

Analysis

All complications will be classified as related to the Optisure RV lead or unrelated.

The following complications will be included in this analysis:

- Cardiac perforation
- Lead dislodgement that occurred greater than 30 days after implant
- Lead insulation damage
- Lead fracture
- Abnormal RV lead performance (abnormal lead defibrillation impedance, abnormal lead pacing impedance, elevated pacing thresholds, loss of capture, failure to deliver therapy, loss of sensing, oversensing, undersensing)

- Other unexpected complications that are considered related to the RV lead

The survival time for all patients will be calculated as the number of days from implant or attempted implant to the date the complication was first discovered. For patients who do not experience a complication related to the Optisure RV lead at the time of their withdrawal, the survival time will be censored on the date of their withdrawal. For patients who have not experienced any complication related to the Optisure RV lead at the time of analysis, the survival time will be censored on the date of analysis. The endpoint will be evaluated using the Kaplan-Meier method and the 95% lower confidence bound (LCB) will be obtained by transformation from its log scale, based on Peto et al¹. The null hypothesis will be rejected if the 95% LCB is greater than 92.5%.

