11.0 Adverse Events

Adverse events are any unfavorable clinical event which impacts, or has the potential to impact the health or safety of a patient caused by or associated with a study device or intervention. Adverse events will be classified as complication or observations.

Complications: Adverse events that require invasive intervention (e.g., lead fracture) with the exception of RV lead perforations. All adverse events reported as RV lead perforations (managed with or without an invasive intervention) will be considered a complication. Each complication will be reported in one of the following categories for analysis purposes:

- RV lead related complication: A complication that is related to the RV lead.
- Device related: A complication related to the device
- Other lead related complication: A complication that is related to the LV or RA lead.
- Procedure related complication: A complication related to an implant or system revision procedure.
- Other complication: Any complication that does not fall into one of the categories listed above.

Observations: Adverse events that can be managed without invasive intervention (e.g., oversensing or loss of pacing capture, which is remedied by reprogramming of the pulse generator). Observations will be reported in one of the following categories:

- RV lead observation: An observation that is related to the RV lead.
- Device related: An observation that is related to the device.
- Other lead related observation: An observation that is related to the LV or RA lead.
- Procedure related observation: An observation that is related to an implant or system revision procedure.
- Other observation: Any observation that does not fall into one of the categories listed above.

Should an adverse event occur at any time between implant and withdrawal, complete an Adverse Event form and submit to St. Jude Medical using the EDC system as soon as possible or within 10 days from the date the site became aware of an event. If an adverse event occurs between scheduled visits, the event should be reported at the next scheduled

visit. Report the adverse event to the IRB/MEC per the IRB/MEC policy. Any explanted devices or leads should be returned to St. Jude Medical for analysis.

Possible adverse events (in alphabetical order) associated with leads, devices or implant and/or system revision procedure may include, but are not limited to the following:

- Abnormal lead defibrillation impedance
- Abnormal lead pacing impedance

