14.0 Deaths

All patient deaths that occur during this investigation must be reported to St. Jude Medical as soon as possible. Notification of death should include a detailed statement of the pertinent events and be signed by the investigator in addition to the appropriate case report forms (Death form, Withdrawal form, and Product Out of Service form). A Mortality Committee will review and classify all patient deaths. It is the investigator's responsibility to notify the IRB/MEC per the IRB/MEC policy. Details of death and the following information, if available, should be provided in a letter to St. Jude Medical by the investigator summarizing the patient's course since enrollment in the study:

- Date and time of death

- Place death occurred (e.g., hospital, nursing home, patients home)
- If death was witnessed
- Identification of the rhythm at the time of death, if known (include any available documentation)
- Cause of death
- Any other circumstances surrounding the death
- Approximate time interval to death from the initiating event.
- Autopsy report (if performed)
- Whether it was device and/or procedure related
- Whether it was related to the study
- Device configuration at the time of death

Provide clinical notes and witness statements. If possible, interrogate the pulse generator. Retrieve and print all episode diagnostics, IEGMs, and programmed parameters. If applicable, the pulse generator should then be programmed OFF.

Every attempt should be made to explant the pulse generator and/or leads intact. Any explanted devices or leads (including damaged leads, lead segments and lead fragments) should be returned to St. Jude Medical for analysis promptly. In the event that the device is not explanted, the above procedure must be followed to retrieve the data. The reason the pulse generator and/or lead(s) are not being returned to St. Jude Medical must be stated clearly on the case report form.

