16.0 Withdrawals

Withdrawal is defined as termination of participation of a patient from a clinical study. All reasonable efforts should be made to retain the subject in the clinical study until completion of the clinical study. Reasons for withdrawal include, but are not limited to the following:

- Patient Death
- Patient and/or Family Request
- Patient Lost to Follow-Up - Defined as the following: Patient will be considered "lost to follow-up" after a minimum of two documented phone calls were made by personnel at the study center to the patient or emergency contact, a certified letter was sent to the last known address, and two consecutive visits pass without an investigator receiving data
- Patient Non-compliance

- Patient Participation terminated by Investigator
- Sponsor Request
- Unsuccessful Implant
- Heart transplant
- Optisure lead removed or capped without a Optisure lead replacement

A Withdrawal Case Report Form should be completed and submitted to St. Jude Medical using the EDC system. **If there is a potential withdrawal in the study, please contact a member of the study team to see if there is anything that can be done to keep the patient in the study.**

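### A death from a lead failure other than perforation, with no invasive intervention, is not clearly a primary-endpoint event and on a literal reading is censored

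*Protocol*

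**What the plan says.** Protocol 4.2 sorts adverse events two ways: "Adverse events are classified as complications or observations". A complication is "An adverse event that requires invasive intervention to resolve (e.g., lead fracture". An observation belongs to the class "Adverse events that can be managed without invasive intervention (e.g., oversensing or loss of pacing capture".

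Protocol 11.0 repeats the complication rule with one carve-out: "Adverse events that require invasive intervention (e.g., lead fracture) with the exception of RV lead perforations". It adds: "All adverse events reported as RV lead perforations (managed with or without an invasive intervention) will be considered a complication". Section 4.2 has no such carve-out.

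Protocol 5.1.1 lists the event types that enter the primary analysis, among them perforation, insulation damage, fracture, failure to deliver therapy and a catch-all. The list is introduced as one of complications. The event is dated at first discovery. For a patient with no lead-related complication at withdrawal, "the survival time will be censored on the date of their withdrawal". The first withdrawal reason in 16.0 is "Patient Death".

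Protocol 14.0 says: "A Mortality Committee will review and classify all patient deaths". Among the details requested, if available, is whether the death was related to the device or the procedure. Relation to the lead is not a separate item. Section 6.2 adds a Kaplan-Meier analysis of all-cause death. No section links the committee's classification to the primary endpoint.

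**The concern.** The test for a complication is whether an intervention is needed to resolve the event. That test works for patients who survive to have a lead revised. It works poorly for the gravest outcome, where the lead fails and the patient dies before anything can be done. Such an event was not resolved by an intervention, and it was not managed without one, so neither class plainly fits.

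If these deaths are treated as withdrawals, Kaplan-Meier handles them as non-informative censoring, although the lead itself caused them. The error has one direction: each such death left out raises the estimated complication-free survival and makes it easier for the lower bound to clear 92.5%. The study exists to characterise chronic lead performance, so the endpoint definition should settle this case.

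The perforation carve-out shows that the intervention test was already seen to miss a serious lead harm. It was repaired for one event type, and in only one of the two places where the definition appears.

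**Working it through.** **1. The possible cases, against the text**

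- *Fatal perforation:* a complication under 11.0 with or without intervention, so an event.
- *Lead complication discovered before death:* an event under 5.1.1, dated at discovery.
- *Fracture or insulation damage found at or after death, no surgery:* arguable. It can be said to have required an intervention that never took place. Section 5.1.1 has no dating rule for discovery after death.
- *Failure to deliver therapy, death, no intervention:* not clearly a complication and not an observation. On a literal reading of 5.1.1 with 16.0 it is censored at death.
- *Death unrelated to the lead:* censored. This is not in dispute.

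**2. The plan's own figures**

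- Mortality (5.2.1): 0.6 × 0.30 + 0.4 × 0.49 = 0.376, stated as 38%.
- Attrition: 1 − (1 − 0.38) × (1 − 0.22) = 0.5164, stated as 52%; 828 / (1 − 0.52) = 1725, as stated.
- Power at n = 645 (Appendix D): with the log-log bound in the printed code, the test passes with at most 37 events. P(Bin(645, 0.05) ≤ 37) = 0.8295, against the printed 0.8324.

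No stated figure is wrong on this point.

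**3. Deaths to be expected**

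- Ignoring other withdrawals: 0.38 × 1725 = 655.5.
- Allowing for the 22% withdrawing for other reasons, with constant hazards: −ln(0.62) = 0.4780 and −ln(0.78) = 0.2485 over 5 years. The share of exits that are deaths is 0.4780 / (0.4780 + 0.2485) = 0.658. Observed deaths: 1725 × 0.5164 × 0.658 ≈ 586.

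**4. Size of the overstatement**

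The protocol gives no lead-related share of deaths. Let s be the assumed share of deaths that are lead-related and uncounted. With an apparent 5-year rate of 95%, the overstatement is 0.95 × (1 − exp(−0.4780 × s)).

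- s = 0.25%: 0.11 points; 586 × 0.0025 ≈ 1.5 deaths uncounted
- s = 1%: 0.45 points; about 5.9 deaths
- s = 2%: 0.90 points; about 11.7 deaths

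The planning margin is 95% − 92.5% = 2.5 points.

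**5. Effect on the test**

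This used 3,000 simulated trials per case: N = 1725, exponential lead events, exponential attrition from 38% death and 22% other withdrawal, and Kaplan-Meier with a log-log lower bound (Greenwood variance). The true rate, counting fatal lead events, was set at exactly 92.5%. An assumed fraction of lead events was fatal and censored.

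- 5% fatal: estimate about 92.9%, chance of wrongly passing about 12%
- 10% fatal: about 93.2%, about 23%
- 20% fatal: about 93.9%, about 60%

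With those deaths counted as events, the chance of wrongly passing is about 4% to 5%.

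On the scale of step 4, the cumulative hazard of lead events is −ln(0.925) = 0.0780. The three fractions are therefore 0.0039, 0.0078 and 0.0156 against 0.4780, or about 0.8%, 1.6% and 3.3% of the assumed mortality. The 20% case lies beyond the range in step 4.

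**The case against.** The definition speaks of an event that requires intervention, not one that received it, and its own example is a type of defect, lead fracture. A fracture or failed therapy delivery that kills before surgery can be said to have required it. Section 4.2 allows only two classes, and a fatal lead failure is plainly not an observation, so complication is the natural remainder. On that view the lead failure is the event and death its outcome. Section 14.0 also provides means of finding the failure: interrogation if possible, return of explanted leads and committee review. How committee classifications feed the endpoint may be set out in an analysis plan or charter that is not at hand.

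Much of this stands. A reader might infer that the protocol excludes lead-related deaths, or that the primary analysis is certain to censor the worst lead outcome. The text does not support that. No section excludes such deaths, and two routes to counting them are already open.

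What remains is that the opposite reading is equally available. Listing failure to deliver therapy in 5.1.1 does not settle it, because the list is of complications and the intervention test still applies. If a general reading of requirement were intended, perforation would hardly need its own exception. Finding a failure after death fixes neither its class nor its date. The event definition and the censoring rule are in the protocol itself, so the ambiguity arises from what the protocol states.

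The objection to the size is also fair. The 0.25% to 2% range has no source in the protocol. At its top, 0.90 points against a planned 5% event rate means about 18 uncounted lead deaths per 100 complications, which nothing in the document suggests. At its bottom, the effect is trivial beside 2.5 points.

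**Conclusion.** The point holds as a gap in the primary event definition. A death from a lead failure other than perforation, with no intervention and no complication discovered beforehand, is not clearly assigned to the endpoint; on a literal reading of 5.1.1 and 16.0 it is censored as event-free. Two careful coders could classify the same death differently.

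The direction of any bias is known: it can only favour the lead. Its size is not. The figure of about 0.1 to 0.9 points rests on an assumed 0.25% to 2% of deaths being lead-related and uncounted, on constant hazards, and on the plan's 38% mortality. The error rates in the simulation rest on assumed fatal fractions in the same way. They show how sensitive the test is near 92.5% and do not forecast what will happen. A reader might infer a bias of known amount, and the protocol gives no basis for one. Nor is the sample size affected: power at n = 645 is unchanged if 95% and 92.5% are kept as the rates for the clarified endpoint.

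The change is cheap and removes a one-directional ambiguity from the primary endpoint, so it should be made.

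**What to change.** - In 4.2, 5.1.1 and 11.0, state that a death adjudicated as related to the Optisure lead is a primary-endpoint event whether or not an intervention took place. Date it at death, unless a lead complication was discovered earlier, in which case the earlier date stands.
- In 14.0, have the Mortality Committee classify relation to the Optisure lead specifically, in addition to the device or procedure relation already requested, and state that this classification feeds the primary analysis.
- In 5.1.1, state that deaths judged unrelated to the lead remain censored.
- Carry the 11.0 perforation exception into 4.2, so that the two definitions agree.

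The cost is one added adjudication category and a few sentences in four sections. The committee already reviews every death. The survival estimate may become slightly less favourable.
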